1. LIST OF ABBREVIATIONS

Table 1: Abbreviations and Specialist Terms

AE	Adverse Event
ANCOVA	Analysis of Covariance
ATC	Anatomical Therapeutic Chemical
AUC	Area Under the Curve
BMI	Body Mass Index
BSA	Body Surface Area
CI	Confidence Interval
CMH	Cochran-Mantel-Haenszel
CRO	Contract Research Organization
CSR	Clinical Study Report
DBL	Database Lock
DLQI	Dermatology Life Quality Index
DMARD	Disease-modifying Antirheumatic Drug
EAIR	Exposure-adjusted Incidence Rate
eCRF	electronic Case Report Form
EQ-5D	EuroQol 5 Dimension
GI	Gastrointestinal
IL	Interleukin
IL	Interleukin
IP	Investigational Product
IPD	Important Protocol Deviation
IRT	Interactive Response Technology
ITT	Intent-to-treat
LOCF	Last Observation Carried Forward
LS	Least-squares
MCMC	Markov Chain Monte Carlo
MedDRA	Medical Dictionary for Regulatory Activities

CC-10004 (Apremilast)

Statistical Analysis Plan. Protocol CC-10004-PPP-001

MI	Multiple Imputation
MMRM	Mixed-effect Model for Repeated Measures
NRI	Non-responder Imputation
NSAIDs	Non-steroidal Anti-inflammatory Drugs
PAO	Pustulotic Arthro-osteitis
PD	Protocol Deviation
PGA	Physician's Global Assessment
PP	Per Protocol
PPP	Palmoplantar pustulosis
PPPASI	Palmoplantar Pustular Area and Severity Index
PPSI	Palmoplantar Severity Index
PT	Preferred Term
Q	Quantile
QoL	Quality of Life
RNA	Ribonucleic Acid
SAP	Statistical Analysis Plan
SD	Standard Deviation
SE	Standard Error
SI	Standard International
SMQ	Standardised MedDRA Querie
SOC	System Organ Class
SRO	Subject's Reported Outcome
TEAE	Treatment-emergent Adverse Event
TNF	Tumor Necrosis Factor
VAS	Visual Analogue Scale
WHO DD	World Health Organization Drug Dictionary

CC-10004 (Apremilast)

Statistical Analysis Plan. Protocol CC-10004-PPP-001

2. INTRODUCTION

This statistical analysis plan (SAP) describes the analyses and data presentations for Amgen's protocol CC-10004-PPP-001 "A Phase 2, Multicenter, Randomized, Double-Blind, Placebo-Controlled, Parallel-Group Study to Evaluate the Efficacy and Safety of Apremilast (CC-10004) in Japanese Subjects with Palmoplantar Pustulosis". It contains definitions of analysis populations, derived variables and statistical methods for the analysis of efficacy and safety.

After all subjects have completed the Week 16 Visit (or discontinued from the study), a Week 16 database restriction will be performed for the primary data analysis. No interim analysis is planned prior to this primary data analysis. At the end of the study, after all subjects have completed, or have been discontinued from the active treatment phase (Weeks 16 to 32) and the post-treatment observational follow-up phase, the final analysis will be performed, and a final clinical study report (CSR) will be generated.

The purpose of the SAP is to ensure the credibility of the study findings by pre-specifying the statistical approaches to the analysis of study data prior to the database restriction and any data analysis for unblinding. This SAP will be finalized and signed prior to unblinding of the Week 16 database. All statistical analyses detailed in this SAP will be conducted using SAS® Version 9.2 or higher.

CC-10004 (Apremilast)

Statistical Analysis Plan. Protocol CC-10004-PPP-001

3. STUDY OBJECTIVES

3.1. Primary Objective

The primary objective is to evaluate the efficacy of apremilast 30 mg twice daily (BID) compared with placebo in Japanese subjects with palmoplantar pustulosis (PPP).

3.2. Secondary Objective

The secondary objective is to evaluate the safety and tolerability of apremilast 30 mg BID compared with placebo in Japanese subjects with PPP.

3.3. Exploratory Objectives

The exploratory objectives are:

[REDACTED]

CC-10004 (Apremilast)

Statistical Analysis Plan. Protocol CC-10004-PPP-001

4. INVESTIGATIONAL PLAN

4.1. Overall Study Design and Plan

[figure not shown]
This is a multicenter, randomized, double-blind, placebo-controlled, parallel-group, Phase 2 study of apremilast in Japanese subjects with PPP and inadequate response to treatment with topical steroid and/or topical vitamin D3 derivative preparations.

This study consists of a screening phase for up to 4 weeks, a 16-week placebo-controlled phase, a 16-week active treatment phase, and a 4-week post-treatment observational follow-up phase at any time the subject completes or discontinues the treatment. To mitigate potential gastrointestinal (GI) side effects (primarily mild to moderate nausea and diarrhea), dose titration (using blister cards) will be implemented over a 5-day period starting at the baseline visit (Week 0) for subjects randomized to apremilast 30 mg BID or Placebo. Subjects randomized to placebo will receive blister cards with dummy dose titration. All subjects will be switched to (or continue with) apremilast 30 mg BID at Week 16 and will maintain this dosing through Week 32. Subjects who discontinue treatment with investigational product (IP: apremilast 30 mg BID or Placebo) or withdraw during the treatment phase will be also asked to enter the 4-week observational follow-up phase after early termination assessment.

Approximately 86 subjects who meet eligibility criteria for the study will be randomized in a 1:1 ratio to one of the two treatment groups. Subject randomization for treatment assignments will be stratified according to a rounded subject's palmoplantar pustular area and severity index (PPPASI) score (≤ 20 / $21-30$ / ≥ 31) at randomization, and whether a subject has any focal infection (yes/no) at randomization.

The study schematic is presented below.

Figure 1: Overall Study Design

CC-10004 (Apremilast)

Statistical Analysis Plan. Protocol CC-10004-PPP-001

4.2. Study Endpoints

4.2.1. Primary Efficacy Endpoint(s)

The primary efficacy endpoint is PPPASI-50 at Week 16: achieving a PPPASI-50 response defined as $\geq 50\%$ improvement in PPPASI total score from baseline at Week 16

4.2.2. Secondary Efficacy Endpoint(s)

The secondary endpoints include below.

Table 2: Secondary Efficacy Endpoints

Assessment	Description	Timeframe
PPPASI: PPPASI-50	Achieving a PPPASI-50 response	By visit in double blind, placebo-controlled phase
PPPASI: PPPASI-75	Achieving a PPPASI-75 response	By visit in double blind, placebo-controlled phase
PPPASI total score	AUC	Week 0-16
	Percent change from baseline.	By visit in double blind, placebo-controlled phase
PPSI total score	AUC	Week 0-16
	Percent change from baseline	By visit in double blind, placebo-controlled phase
PGA score for palms and soles	Change from baseline	By visit in double blind, placebo-controlled phase
	Achieving a PGA score of cleared (0) or minimal (1)	By visit in double blind, placebo-controlled phase
	Achieving a PGA score of cleared (0) or minimal (1) with at least a 2-grade improvement	By visit in double blind, placebo-controlled phase
SRO: Subject's VAS assessment for PPP symptoms	Change from baseline	By visit in double blind, placebo-controlled phase (except for baseline)
AUC = Area under the curve; PGA = Physician's Global Assessment; PPP = Palmoplantar Pustulosis; PPPASI = Palmoplantar Pustular Psoriasis Area Severity Index; PPPASI-50 = defined as $\geq 50\%$ improvement in PPPASI total score from baseline; PPPASI-75 = defined as $\geq 75\%$ improvement in PPPASI total score from baseline; PPSI = Palmoplantar Severity Index; SRO: Subject's Reported Outcome; VAS = Visual Analogue Scale.		

4.2.3. Exploratory Efficacy Endpoint(s)

The exploratory endpoints include below.

CC-10004 (Apremilast)

Statistical Analysis Plan. Protocol CC-10004-PPP-001

**Table 3: Exploratory Efficacy Endpoints**

Assessment	Description	Timeframe
PPPASI: Three sub scores (Erythema, Pustules/Vesicle, Desquamation/Scale)	Change from baseline of individual sub scores	By visit in double blind, placebo-controlled phase, active treatment phase and follow-up
Modified PPPASI: modified PPPASI-50	Achieving a modified PPPASI-50 response	By visit in double blind, placebo-controlled phase, active treatment phase and follow-up
Modified PPPASI: modified PPPASI-75	Achieving a modified PPPASI-75 response	By visit in double blind, placebo-controlled phase, active treatment phase and follow-up
Modified PPPASI total score	AUC	Week 0-16
Modified PPPASI: Two sub scores (Pustules, Vesicle)	Percent change from baseline	By visit in double blind, placebo-controlled phase, active treatment phase and follow-up
	Change from baseline of individual sub scores	By visit in double blind, placebo-controlled phase, active treatment phase and follow-up
SRO: Subject's assessment for each sign/finding of PPP (Erythema, Pustules/Vesicle and Desquamation/Scale) (PPSI scale is used for assessment)	Change from baseline	By visit in double blind, placebo-controlled phase, active treatment phase and follow-up
SRO: DLQI	Change from baseline	Week 8, 16, 24 and 32
SRO: EQ-5D	Change from baseline of the utility index and VAS score	Week 8, 16, 24 and 32
PPPASI: PPPASI-50	Achieving a PPPASI-50 response	By visit in active treatment phase
PPPASI: PPPASI-75	Achieving a PPPASI-75 response	By visit in active treatment phase
PPPASI total score	Percent change from baseline	By visit in active treatment phase
PPSI total score	Percent change from baseline	By visit in active treatment phase
PGA score for palms and soles	Change from baseline	By visit in active treatment phase
	Achieving a PGA score of cleared (0) or minimal (1)	By visit in active treatment phase
	Achieving a PGA score of cleared (0) or minimal (1) with at least a 2-grade improvement	By visit in active treatment phase

CC-10004 (Apremilast)

Statistical Analysis Plan. Protocol CC-10004-PPP-001

Assessment	Description	Timeframe
SRO: Subject's VAS assessment for PPP symptoms	Change from baseline	By visit in active treatment phase

AUC = Area under the curve; DLQI = Dermatology Life Quality Index; EQ-5D = EuroQol 5 Dimension; modified PPPASI-50 = defined as $\geq 50\%$ improvement of modified PPPASI total score from baseline; modified PPPASI-75 = defined as $\geq 75\%$ improvement of modified PPPASI total score from baseline; PGA = Physician's Global Assessment; PPP = Palmoplantar Pustulosis; PPPASI = Palmoplantar Pustular Psoriasis Area Severity Index; PPPASI-50 = defined as $\geq 50\%$ improvement in PPPASI total score from baseline; PPPASI-75 = defined as $\geq 75\%$ improvement in PPPASI total score from baseline; PPSI = Palmoplantar Severity Index; SRO: Subject's Reported Outcome; VAS = Visual Analogue Scale.

Additional exploratory endpoints include below.

- Time to response for PPPASI-50 and PPPASI-75

4.2.4. Derivation of Efficacy Endpoints

The definition and derivation of efficacy endpoints are described below and in the appendices of the protocol. Change from baseline is calculated as post-baseline visit value - the baseline value. Percent change from baseline is defined as $100 \times \text{change from baseline}/\text{baseline value} (\%)$. Baseline definition for all efficacy endpoints is given in [Section 5.3](#). Handling of time points is described in [Section 5.4](#).

4.2.4.1. PPPASI

The PPPASI is a disease-specific efficacy assessment tool used by investigators for assessing and grading the severity and area of palmoplantar pustulosis lesions and their response to therapy. PPPASI is established to detect a change of disease status on palms or soles. The right/left palm and right/left sole are evaluated for 3 signs of the disease (erythema, pustules/vesicle and desquamation/scale) as sub-scores. PPPASI produces numeric scores that can range from 0 to 72 and a higher score indicates more severe disease.

In the PPPASI system, the palms and soles are divided into 4 regions: the right palm, left palm, right sole, and left sole, which account for 20%, 20%, 30%, and 30% of the total body surface area (BSA) of the palms and soles, respectively. Each of these areas is assessed separately for erythema, pustules and desquamation, which are each rated on a scale of 0 to 4.

The scoring system for the signs of the disease (E = erythema, P = pustules/vesicle and D = desquamation/scale) is: 0 = none, 1 = slight, 2 = moderate, 3 = severe, and 4 = very severe.

The scale for estimating the area of involvement for pustular lesions is outlined below.

0 = no involvement, 1 = 1% to 9% involvement, 2 = 10% to 29% involvement, 3 = 30% to 49% involvement, 4 = 50% to 69% involvement, 5 = 70% to 89% involvement, and 6 = 90% to 100% involvement

The PPPASI total score formula is:

CC-10004 (Apremilast)

Statistical Analysis Plan. Protocol CC-10004-PPP-001

PPPASI total score = $(E + P + D) \times \text{Area} \times 0.2$ (right palm) + $(E + P + D) \times \text{Area} \times 0.2$ (left palm) + $(E + P + D) \times \text{Area} \times 0.3$ (right sole) + $(E + P + D) \times \text{Area} \times 0.3$ (left sole)

4.2.4.1.1. PPPASI-50, 75

PPPASI-50 and PPPASI-75 are defined as $\geq 50\%$ and $\geq 75\%$ improvement in PPPASI total score from baseline, respectively.

4.2.4.1.2. AUC for PPPASI total score

The AUC for PPPASI total score from baseline through a timepoint is the sum of the AUCs in each time interval specified by the dates of the visits. The individual AUC for any given time interval is calculated based on the linear trapezoidal method, which uses linear interpolation between data points to calculate the AUC. The AUC_{wk16} which is AUC from baseline (Visit 2/Day 1) through Week 16 (Visit 10/Day 113) is given by

$$AUC_{wk16} = \frac{113}{(t_{10} - t_2)} \times \sum_{i=2}^{10-1} \frac{1}{2} (S_i + S_{i+1})(t_{i+1} - t_i)$$

where S_i = PPPASI total score for i_{th} visit and t_i = PPPASI assessment dates of i_{th} visit. When Week 16 does not exactly coincide with the target Day 113, the AUC through Week 16 will be adjusted for the actual study duration by dividing the total AUC by total study duration (in days) and multiplying this quantity by 113 days.

4.2.4.1.3. PPPASI sub-scores (Erythema, Pustules/Vesicle, Desquamation/Scale)

The PPPASI sub-score is defined the PPPASI total score including only one sub-domain (E = erythema, P = pustules/vesicle or D = desquamation /scale). For example, score of erythema as PPPASI sub-score will be calculated as below.

PPPASI sub-score (Erythema) = $(E) \times \text{Area} \times 0.2$ (right palm) + $(E) \times \text{Area} \times 0.2$ (left palm) + $(E) \times \text{Area} \times 0.3$ (right sole) + $(E) \times \text{Area} \times 0.3$ (left sole)

4.2.4.2. Modified PPPASI

Modified PPPASI is an exploratory disease-specific efficacy assessment by investigators, which emphasizes on pustules and vesicles. The right/left palm and right/left sole are evaluated for 4 signs of the disease (E = erythema, P = pustules, V = vesicle and D = desquamation/scale) as sub-scores. The development of vesicles followed by pustule in palm and sole is distinctive pathophysiology in PPP. Modified PPPASI is modified from PPPASI by distinguishing between pustules and vesicle. The range of modified PPPASI score is from 0 to 96. A higher score indicates more severe disease.

The modified PPPASI formula is:

Modified PPPASI total score = $(E + P + V + D) \times \text{Area} \times 0.2$ (right palm) + $(E + P + V + D) \times \text{Area} \times 0.2$ (left palm) + $(E + P + V + D) \times \text{Area} \times 0.3$ (right sole) + $(E + P + V + D) \times \text{Area} \times 0.3$ (left sole)

CC-10004 (Apremilast)

Statistical Analysis Plan. Protocol CC-10004-PPP-001**4.2.4.2.1. Modified PPPASI-50, 75**

Modified PPPASI-50 and Modified PPPASI-75 are defined as $\geq 50\%$ and $\geq 75\%$ improvement in Modified PPPASI total score from baseline, respectively.

4.2.4.2.2. AUC for modified PPPASI total score

The AUC for modified PPPASI total score is similarly defined as the AUC for PPPASI ([Section 4.2.4.1.2](#)).

4.2.4.2.3. Modified PPPASI sub-scores (Pustules, Vesicle)

The modified PPPASI sub-score is similarly defined as the PPPASI sub-scores ([Section 4.2.4.1.3](#)). The modified PPPASI sub-score for erythema and desquamation/scale are same as the PPPASI sub-score for erythema and desquamation/scale, respectively.

4.2.4.3. PPSI

PPSI is a disease-specific efficacy assessment tool used by investigators for assessing and grading the severity of palmoplantar pustulosis lesions and their response to therapy. In the PPSI system, evaluation skin lesion sites are identified by either palms or soles, which has the most severe skin lesion at screening. Any identified skin lesion site will be assessed at all subsequent visits. Evaluation of skin lesion sites are assessed separately for erythema, pustules/vesicle and desquamation/scale, which are each rated on a scale of 0 to 4. The PPSI produces a numeric score that can range from 0 to 12. A higher score indicates more severe disease.

The severity of the disease is calculated as follows.

The scoring system for the signs of the disease (E: erythema, P: pustules/vesicle: and D: desquamation/scale) is: 0 = none, 1 = slight, 2 = moderate, 3 = severe, and 4 = very severe.

The total score will be calculated by: PPSI total score= (E + P + D)

4.2.4.3.1. AUC for PPSI total score

The AUC for PPSI total score is similarly defined as the AUC for PPPASI ([Section 4.2.4.1.2](#)).

4.2.4.4. Subject's assessment for each sign/finding of PPP (Erythema, Pustules/Vesicle and Desquamation/Scale of PPSI scale)

A subject's assessment for each sign/finding on hands or feet (erythema, pustules/vesicles and desquamation/scale) are an exploratory disease-specific efficacy assessment. Worst status by a subject's own assessment between visits will be recorded. A part of PPSI assessment is used as a questionnaire. A subject will evaluate skin lesion sites which has the most severe skin lesion assessed by an investigator for evaluation of PPSI at screening. Any identified skin lesion site will be assessed at all subsequent visits.

A numeric score is produced for each sign/finding of PPP and the range is from 0 to 4 (0 = none, 1 = minimal, 2 =moderate, 3 = severe, and 4 = very severe) and the total score will be 0 to 12.

CC-10004 (Apremilast)

Statistical Analysis Plan. Protocol CC-10004-PPP-001**4.2.4.5. PGA for palms and soles**

PGA for palms and soles is a physician's global assessment localized to palms and soles, which is skin lesions of PPP. Physician's global assessment is commonly used for assessment of the intervention. PGA for palms and soles also produces numeric score that can range from 0 to 5. A higher score indicates more severe disease.

Lesions on palms and soles will be graded based on the scales: 0 = Clear, 1 = Almost clear, 2 = Mild, 3 = Moderate, 4 = Severe, 5 = Very severe

4.2.4.6. Subject's VAS Assessment for PPP Symptom

VAS is a tool used to help a person to rate the intensity of certain sensations and feelings, such as pain. Each score ranges from 0 to 100. The left-hand boundary (0) represents no itch/pain and the right-hand boundary (100) represents itch/pain as severe as can be imagined. Subject assesses a degree of pruritus and pain as symptoms on hands and feet caused by PPP. Worst status by a subject's impression between visits will be recorded. PPP-related symptoms should be included in these assessments.

4.2.4.7. DLQI

The DLQI is a Quality of Life (QoL) questionnaire for use in a dermatology clinical setting to assess limitations related to the impact of skin disease. The instrument contains 10 items pertaining to the subject's skin status over the last one week.

With the exception of the item number 7, the subject responds on a four-point scale, ranging from "Very Much" (score 3) to "Not at All" or "Not relevant" (score 0). The item number 7 is a multi-part item, the first part of which ascertains whether the subject's skin prevented them from working or studying (Yes or No, score 3 or 0 respectively), and if "No," then the subject is asked how much of a problem the skin has been at work or study over the past week, with response alternatives being "A lot," "A little," or "Not at all" (score 2, 1, or 0 respectively). The DLQI total score is derived by summing all item scores, which has a possible range of 0 to 30, with 30 corresponding to the worst quality of life, and 0 corresponding to the best.

The DLQI can be grouped into six subscales: symptoms and feelings; daily activities; leisure; work/school; personal relationships; and treatment. Scores for four of the subscales (symptoms and feelings, daily activities, leisure, and personal relationships) range from 0 to 6; scores for two of the subscales (work/school and treatment) range from 0 to 3. Higher scores indicate more severe disease and correspond to poorer quality of life.

4.2.4.8. EQ-5D

EQ-5D is a general and comprehensive QoL questionnaires which assesses the subject status on the visit day. The EQ-5D is a generic health status measure composed of a descriptive system which comprises the 5 dimensions (mobility, self-care, usual activities, pain/discomfort and anxiety/depression) each of which has 5 levels: no problems, slight problems, moderate problems, severe problems and unable, and a VAS asking individuals to rate their own health on a vertical, visual analog scale where the endpoints are labeled 'Best imaginable health state' (score of 100) and 'Worst imaginable health state' (score of 0). EQ-5D health states will be converted into a single index value by applying country specific value set ([Ikeda, 2015](#)).

CC-10004 (Apremilast)

Statistical Analysis Plan. Protocol CC-10004-PPP-001

4.2.5. Safety Endpoints

Safety endpoints will include:

- Treatment-emergent adverse event (TEAE): type, frequency and incidence rate, severity, and relationship of TEAEs to IP
- Clinically significant changes in body weight, vital signs, and/or laboratory findings

4.3. Stratification, Randomization, and Blinding

At Visit 2 (Week 0 [Day 1]), subjects who meet eligibility criteria will be randomized using a permuted block randomization in parallel with 1:1 ratio to receive either apremilast 30 mg BID or placebo, using a centralized Interactive Response Technology (IRT). Eligible subjects will be stratified according to a subject's rounded PPPASI score (≤ 20 / 21-30 / ≥ 31) at randomization and whether a subject has or not any focal infection (yes/no) at randomization.

This study will be conducted as a double-blind study for the placebo-controlled treatment phase. During the active treatment phase, the IP will remain blinded, to prevent study personnel and subjects from knowing the IP assignment in the placebo-controlled phase. After 16 weeks of treatment, all subjects originally randomized to the placebo arm at the baseline visit will be switched to receive apremilast 30 mg BID.

The primary data analysis will be conducted after all subjects have completed the Week 16 visit (or discontinued from the study). However, unblinded data will only be made available to selected sponsor and contract research organization (CRO) team members involved with analysis of the data. Prior to the primary data analysis, the selected sponsor and CRO team members will be required to give their consent to declare not to disclose any subject-level data to maintain the data integrity of this study. All other sponsor, site, and CRO personnel directly involved with the conduct of the study, will remain blinded to treatment assignments until the final database lock at the end of the study.

4.4. Sample Size Determination

A total of approximately 86 subjects will be randomized 1:1 ratio to receive apremilast 30 mg BID or placebo. The study has 80% power (based on a chi-square test at a 2-sided significance level of 0.10) to demonstrate the superiority of apremilast 30 mg BID over placebo with respect to the primary endpoint of PPPASI-50 at Week 16, assuming the PPPASI-50 rates of 45% (apremilast 30 mg BID) and 20% (placebo), respectively. The PPPASI-50 rate of 20% at Week 16 in placebo is based on the PPPASI-50 placebo rate of 21% at Week 16 in guselkumab Phase 2 study ([Terui, 2018](#)). Considering at least 20% difference as a clinically meaningful difference, apremilast 30 mg BID PPPASI rate of 45% is expected in this study. The sample-size was estimated using SAS 9.4 power procedure.

For the skin biopsy RNA expression analysis, N=13 subjects per arm will provide 80% probability to observe the lower limit of the 90% confidence interval (CI) of a decrease of IL8 mRNA expression from baseline to Week 16 in the apremilast treated arm is over -44%, based on the mean and standard deviation (SD) change observed in a 12 weeks apremilast psoriasis study CC-10004-PSOR-004 ([Gottlieb, 2013](#)). For the serum protein biomarker analysis, N=17 subjects per arm will provide 80% probability to observe the lower limit of the 90% CI of an

CC-10004 (Apremilast)

Statistical Analysis Plan. Protocol CC-10004-PPP-001

absolute difference of decrease from baseline to Week 16 of IL17A levels in the apremilast arm is over 60%, based on the mean and SD change observed in the psoriasis study in Japan, CC-10004-PSOR-011 ([Garcet, 2018](#)).

CC-10004 (Apremilast)

Statistical Analysis Plan. Protocol CC-10004-PPP-001

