#### **1.3.5. Rationale for Pharmacodynamics and Predictive Biomarkers**

Although several pathogeneses of PPP such as concomitant tonsillitis, periodontitis or metal allergy have been proposed, the etiology of PPP remains unknown.

Recently, pathophysiology of PPP at skin lesion (from vesicle formation to pustule development via pustulo-vesicle) is reported that shows serum IL17, IL22, TNF $\alpha$ , and IL8 are elevated in serum in PPP patients (Murakami, 2011) and IL-36 pathway and neutrophil gene expression (IL8, CXCL1, IL17A, IL36G, IL12A, IL17F, IL22, IL23B, DEFB4A, TNF $\alpha$ ) in the pustular skin is also reported (Murakami, 2011; Liang, 2017).

Evidence of an anti-neutrophil effect in lesioned skin from psoriasis patients was observed after apremilast 20 mg BID treatment for 12 weeks resulted in a 44% decrease in IL8 messenger RNA (mRNA) levels (N=15, p=0.018) (Gottlieb, 2013).

Based on those results, the following hypotheses are expected.

1. Apremilast will significantly reduce the serum IL17A protein level as part of suppressed Th17 response
2. Apremilast will significantly reduce expression of IL8 mRNA as marker of neutrophils at the pustular skin

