After all subjects have completed the Week 16 Visit (or discontinued from the study), a Week 16 database restriction will be performed, and the primary data analysis will be conducted. However, unblinded data will only be made available to selected Sponsor and contract research organization (CRO) team members involved with analysis of the data. All other Sponsor, site, and CRO personnel directly involved with the conduct of the study, will remain blinded to treatment assignments until the final database lock at the conclusion of the study.

All subjects will be switched to (or continue with) apremilast 30 mg BID at Week 16 and will maintain this dosing through Week 32.

Observational Follow-up evaluation will be performed 4 weeks after last dose of IP. Subjects who discontinue treatment with IP or withdraw during the Treatment Phase will be also asked to enter the 4-week Observational Follow-up Phase after Early Termination assessment.

An interim Analysis is not planned. An independent committee (eg, steering committee, data monitoring committee, safety monitoring committee) is also not planned. At the end of the study, after all subjects have completed, or have been discontinued from the active treatment phase (Weeks 16 to 32) and the post-treatment observational follow-up phase, the final analysis will be performed, and a final clinical study report will be generated.

The efficacy, safety, and pharmacodynamic assessments to be performed during the study are outlined in the Schedule of Assessments ([Table 5](#)). [REDACTED] are an optional measurement for a subset of subjects who agree to additional informed consent (IC) at limited clinical study sites.

The study will be conducted in compliance with the ICH of Technical Requirements for Registration of Pharmaceuticals for Human Use/Good Clinical Practice (GCP) and applicable regulatory requirements.

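### The 80% stated for the 13-per-arm skin-biopsy sizing does not follow from the printed -44% threshold and the 44% IL8 decrease in the protocol

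*SAP*

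**What the plan says.** SAP 4.4 says that "N=13 subjects per arm will provide 80% probability to observe the lower limit of the 90% confidence interval (CI) of a decrease of IL8" mRNA from baseline to Week 16 "in the apremilast treated arm is over -44%, based on the mean and standard deviation (SD) change observed" in a 12-week psoriasis study. Protocol 9.3 gives the same N, probability, interval and threshold. Neither section prints the mean or the SD.

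Protocol 1.3.5, citing the same publication, reports evidence from psoriasis skin "after apremilast 20 mg BID treatment for 12 weeks resulted in a 44% decrease in IL8 messenger RNA (mRNA) levels (N=15, p=0.018"). It does not say whether 44% is an arithmetic mean, a geometric mean or a median, and it does not name the test behind the p-value. The hypothesis set out there is "Apremilast will significantly reduce expression of IL8 mRNA as marker of neutrophils at the pustular skin".

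The paragraph that sizes the biopsy analysis also sizes the serum IL17A analysis on the same pattern: N=17 per arm, 80%, lower limit of the 90% CI over 60%. Protocol 3.1 describes measurements, whose name is blacked out, that "are an optional measurement for a subset of subjects who agree to additional informed consent (IC) at limited clinical study sites". The biopsy analysis appears to be among them.

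**The concern.** The threshold has the same size as the only reported effect. A confidence limit is rarely beyond the value on which the interval is centred, so an 80% chance of clearing that value is not credible without further explanation. Either the threshold, the probability or the assumed planning mean is something other than what a reader would take from the text.

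As printed, a reader cannot tell which event the 80% describes. The biopsy result also cannot be judged against the sizing claim, because the threshold coincides with the earlier estimate. Only the rationale for the size of an exploratory subset is at stake.

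**Working it through.** **Inputs**

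- SAP 4.4 and Protocol 9.3: n=13, 80%, 90% CI, threshold -44%, a within-arm change.
- Protocol 1.3.5: 44% decrease, N=15, p=0.018.
- Assumption A: 44% is the planning mean.
- Assumption B: the SD can be recovered from that p-value. The test is unnamed, so four versions are carried.

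**Step 1. Back-calculated SD** = 44 × √15 / c

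| Test assumed | c | SD |
|---|---|---|
| two-sided t(14) | 2.678 | 63.6 |
| two-sided z | 2.366 | 72.0 |
| one-sided t(14) | 2.319 | 73.5 |
| one-sided z | 2.097 | 81.3 |

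**Step 2. The printed criterion at n=13**

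(a) *Signed change, roughly normal data.* The mean is -44 and the threshold is -44. The 90% limit lies c × SE from the sample mean, with c the 95th percentile. So P(lower limit > -44) = P(upper limit < -44) = 5%, whatever the SD. The opposite direction gives 95%.

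(b) *Decrease coded positive, threshold literally -44.* The distance from mean to threshold is 44 + 44 = 88. With a t-interval the probability is 99.9% at SD 63.6 and 97.9% at SD 81.3. To bring it down to 80% the SD must be about 120. At N=15 that gives t = 44 × √15 / 120.2 = 1.42 and p of about 0.18, against the reported 0.018.

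(c) *Lognormal data, interval on the log scale.* The post/pre ratio has mean 0.56 and SD s (0.636 to 0.813). Then σ² = ln(1 + (s/0.56)²) and μ = ln 0.56 - σ²/2. The distance from μ to ln 0.56 is σ/2 in SD units. For s=0.636, σ=0.910 and the noncentrality is √13 × 0.455 = 1.64, which gives 46%. The other three SDs, in table order, give 51%, 52% and 57%. If the 44% is already a geometric-mean decrease, this returns to 5%.

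(d) *Lognormal data, raw-scale t-interval (simulated).* The CI shows a decrease of at least 44% in 17% to 21% of runs. The numerical lower limit is above -44% in under 1%.

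None of these is 80%.

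**Step 3. A candidate criterion: 90% CI excludes 0**

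With SD 63.6, the effect size is 44/63.6 = 0.692. By normal approximation, n = ((1.645 + 0.842)/0.692)² = 12.93 (unrounded inputs), so 13. The probability at n=13 is Φ(0.692 × √13 - 1.645) = 80.2%. Both printed figures are recovered. The match does not carry over to the other pairings:

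| SD | Normal approximation | t-interval |
|---|---|---|
| 63.6 | 80.2% | 75.9% |
| 72.0 | 71.1% | 66.7% |
| 73.5 | 69.7% | 65.2% |
| 81.3 | 62.1% | 57.8% |

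For the lognormal model of (c) analysed on the log scale, the exclude-0 probability is about 98%.

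**The case against.** The planning mean and SD come from a publication that is not available here, and the protocol does not call 44% a mean. The biomarker sections are largely blacked out, so the criterion, scale and interval type may be stated there. This stands: the calculation is conditional on Assumption A, and the inputs cannot be called absent from the full plan. The sizing sentence itself is fully visible in both documents, however, and it pairs a probability with a threshold that the visible figures do not support.

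The sign convention is also open, and the 5% result needs raw-scale normality. This stands too. On the log scale the criterion is attainable and depends on N, reaching 80% at N=24 to 32 for the four SDs. It would therefore be wrong to say that it cannot be met at any sample size. It still does not give 80% at N=13.

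One event does come close to 80%. With lognormal data and a raw-scale t-interval, the upper limit of the change lies above -44% in 79% to 83% of runs. That event means only that the interval fails to show a 44% decrease, so it is not a plausible aim for sizing.

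A reader might infer that the threshold is simply a misprint for 0 and that N=13 is right. The documents do not establish this. The match in Step 3 combines a t-based SD with a normal-approximation power and is one of eight pairings. The log scale gives a different answer. The IL17A sentence also uses a non-zero threshold although its hypothesis is likewise a significant reduction, so a deliberate non-zero threshold cannot be excluded.

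**Conclusion.** The concern holds as a minor mismatch between a stated probability and the documents' own figures. If the planning mean is the 44% decrease, the printed criterion has a probability at N=13 of about 5% or 95% (signed change, normal data), 98% to 99.9% (decrease coded positive), or 46% to 57% (lognormal, log scale). None is the stated 80%. The 5% and 95% do not depend on the SD; the other ranges rest on the back-calculated SDs of 63.6 to 81.3.

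That a 90% CI excluding 0 was intended is one possible explanation and no more. Two further inferences are not supported. One is that 13 per arm is too few, because the intended criterion is unknown. The other is that the trial must show a 44% IL8 reduction, because no visible passage makes -44% a success criterion. The point is confined to the exploratory biopsy sizing; the primary endpoint and N=86 are untouched.

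**What to change.** In Protocol 9.3 and SAP 4.4, replace the threshold and the probability with the criterion actually used in the sizing calculation and the probability at N=13 that follows from it. State the planning mean, SD, scale (raw percent or log) and interval type in the same sentence. If these already stand in the blacked-out biomarker text, bring them into the sizing sentence so that the two agree. The sponsor must supply the criterion; none of the probabilities worked out above should be inserted as a substitute for it.

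The cost is one sentence in each document. No subjects need be added and no analysis changes.
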